5.3. Per Protocol Set

The Per Protocol Set (PPS) will include all randomised patients who receive at least one dose of the study drug, have at least one post-Baseline EASI assessment, and additionally for whom there are no important protocol deviations affecting efficacy at Week 16. Patients will be analysed under the treatment group as randomised.

The precise reasons for excluding patients from the PPS population, and other pre-defined data handling issues will be fully defined and documented in the corresponding Blind Data Review Meeting (BDRM) reports, finalised before unblinding of the study.

5.4. Protocol Deviations

Any protocol deviations during the conduct of the trial will be recorded by CRA/Monitors as detected or derived from data collected in the clinical database. Protocol deviations are categorized as non-important or important and finalized during BDRM before database lock.

Protocol deviations affecting primary efficacy will be defined and reviewed before the BDRM and closed during the BDRM, to be held (with report finalized) before database lock.

All patients enrolled (those who signed the informed consent) will be described in the summaries of patient disposition, and will be used for some patient listings.

This document is confidential.

6. Estimands and Data Handling for Efficacy Analyses

As discussed in Protocol Section 11.8.1, the primary analyses for efficacy will be based on the FAS. Furthermore, the primary and key secondary efficacy variables will be also analysed for the overall population using the PPS population to assess the robustness of the findings from the FAS population. As CCI [REDACTED], all efficacy endpoints will be analysed as well by previous exposure to dupilumab (Yes/No).

6.1. Primary Efficacy Analysis (Overall Population)

6.1.1. Primary and Key Secondary Efficacy Endpoints

The primary efficacy analysis will be based on the main estimand for the overall population (FAS). The objectives, variables and population-level summary measures for the main estimand for the primary efficacy endpoint and key secondary endpoints is provided in table below:

Objectives/Treatment Condition of Interest	Variable/Outcome Assessed	Population-Level Summary Measure
To evaluate the efficacy of lebrikizumab compared with placebo in patients not adequately controlled with cyclosporine or for whom cyclosporine is not medically advisable up to Week 16 (ie, at the end of the Induction Period).	Title: EASI 75, IGA(0/1) and 2pt improvement, 4pt improvement in Pruritus NRS Description: Patient achieving: EASI 75: $\geq 75\%$ reduction in EASI score from Baseline, IGA: IGA score of 0 or 1 with 2pt improvement from baseline, Pruritus NRS: 4pt improvement from baseline Time Frame: 16 weeks	Population: Adult and Adolescent Patients with Moderate-To-Severe AD that are not Adequately Controlled with Cyclosporine or for whom Cyclosporine is not Medically Advisable. Measure: Difference between treatments (lebrikizumab minus placebo) in proportion of patients achieving EASI 75, IGA criteria, pruritus NRS criteria at Week 16

Abbreviations: AD = atopic dermatitis; EASI = Eczema Area and Severity Index (score); IGA = Investigator Global Assessment; NRS = Numerical Rating Scale.

The following ICEs are envisioned during the study, to be considered up to and including the Week 16 assessment:

- ICE1: Patient prematurely discontinues study treatment due to reasons other than lack of efficacy prior to Week 16.
- ICE2: Patient prematurely discontinues study treatment due to lack of efficacy prior to Week 16.
- ICE3: Patient receives rescue medication prior to Week 16 (either allowed or prohibited) for treatment of AD

Treatment discontinuation due to pandemic will be treated under the same intercurrent event as treatment discontinuation due to reasons other than lack of efficacy. Intermittent missing assessment due to pandemic and/or related restrictions will be treated the same as any other intermittent missing values. Details of how missing data will be handled for efficacy are described in [Section 6.3](#).

For supportive analyses a second estimand will be used.

This document is confidential.

The ICEs will be handled using the following approaches to be applied under the main and second estimands.

Estimand	Analysis Strategy for ICEs		
	Treatment Discontinuation due to:		ICE3: Rescue or Prohibited Meds for Treatment of AD
	ICE1: Reasons Other than Lack of Efficacy	ICE2: Lack of Efficacy	
Main Estimand (Hybrid)	Hypothetical Strategy: Set to missing	Composite Strategy: Set to baseline	Composite Strategy: Set to baseline
Second Estimand: Categorical Endpoints (Composite)	Composite Strategy: Set to non-responder	Composite Strategy: Set to non-responder	Composite Strategy: Set to non-responder

Abbreviation: ICE = intercurrent event; AD = atopic dermatitis.

Details on missing data imputation are described in Section エラー! 参照元が見つかりません。.

Main Estimand (Hybrid):

- The approach for the main estimand is a hybrid estimand representing the primary clinical question of interest: what is the difference between treatment conditions, ie, Lebrikizumab vs Placebo, in the target patient population, in successful responses after 16 weeks achieved without use of rescue medication and if all patients continued with treatment except those who discontinued due to lack of efficacy?

Second Estimand:

- The second estimand for categorical endpoints is a composite estimand representing the supportive clinical question of interest: what is the difference between treatment conditions in the target patient population, in successful responses after 16 weeks achieved without use of rescue medication or treatment discontinuation?

The complementary estimand approach here allows for an estimate of the effects of the different events to be ascertained.

6.1.2. All Other Secondary and Other Efficacy Endpoints

All binary other secondary and other efficacy endpoints will be analysed using the same methodology as described in [Section 6.1.1](#) for the primary efficacy endpoint using only the main estimand. Sensitivity analyses based on the PPS population will not be conducted for these endpoints.

Continuous other secondary endpoints assessed at multiple post-baseline visits during the Induction Period will be analysed on the following estimands:

Estimand	Analysis Strategy for ICEs		
	Treatment Discontinuation due to:		ICE3: Rescue or Prohibited Meds for Treatment of AD
	ICE1: Reasons Other than Lack of Efficacy	ICE2: Lack of Efficacy	
Main Estimand (Hybrid)	Hypothetical Strategy: Set to missing	Composite Strategy: Set to baseline	Composite Strategy: Set to baseline
Second Estimand: Continuous Endpoints (Hypothetical)	Hypothetical Strategy: Set to missing	Hypothetical Strategy: Set to missing	Hypothetical Strategy: Set to missing

Abbreviation: ICE = intercurrent event; AD = atopic dermatitis.

This document is confidential.

6.2. Subgroup Efficacy Analyses (Dupilumab Naïve and Patients Previously Exposed to Dupilumab)

The same estimands as per [Section 6.1](#) will also be conducted for the subgroup analyses, for [CCI](#) purposes.

6.3. Imputation Process for Estimand Handling and Missing Data

Imputation for missing data will occur for primary and key secondary efficacy endpoints.

Where the endpoint is a binary or categorical outcome, the imputation will occur on the binary/categorical outcome.

The following data imputation methods will be employed:

Estimand	Handling Strategy: Imputation
Primary and Key Secondary Efficacy Endpoints	
Main Estimand	
Composite Strategy: Set to baseline (BOCF)Hypothetical Strategy: Set to missing and impute with Markov Chain Monte-Carlo (MCMC) multiple imputation (MI)Missing data not affected by ICE: MCMC MI
Second Estimand: Categorical Endpoints	
Composite Strategy: Set to non-responder (NRI)Missing data not affected by ICE: NRI
Other Secondary and Other Efficacy Endpoints	
Estimand for Categorical Endpoints	
As per main estimand for primary and key secondary efficacy endpoints
Main Estimand for Continuous Endpoints	
As per main estimand for primary and key secondary efficacy endpoints
Second Estimand for Continuous Endpoints	
Hypothetical strategy: Set to missing and do not impute (MMRM)Missing data not affected by ICE: do not impute (MMRM)

Abbreviations: ICE = Intercurrent Event; MCMC = Markov-Chain Monte-Carlo; MI = Multiple Imputation; BOCF, Baseline-Observation-Carried-Forward; NRI = Non-Responder Imputation; MMRM, Mixed Effect Model for Repeated Measures.

Where imputation occurs, imputation will be based on the overall population, and subsequent subgroup analyses (dupilumab naïve and previously exposed to dupilumab) will utilise these imputed data, selecting only the required patients for the analysis.

Where missing data are to be imputed for efficacy using the approaches above, a summary table by week of the frequency and type of missing data will be presented.

General MI Approach ([Section 6.3.1](#)) will be used for

- Main estimand of the primary and key secondary efficacy endpoints
- Main estimand for categorical other secondary efficacy endpoints
- Continuous Other Secondary Efficacy Endpoints

Non-Responder Imputation Approach ([Section 6.3.2](#)) will be used for the Second estimand of the primary and key secondary efficacy endpoints.

This document is confidential.

Mixed Model for Repeated Measures analyses ([Section 6.3.3](#)) will be performed on second estimand for continuous other secondary efficacy endpoints.

6.3.1. General Multiple Imputation Approach

The primary method of imputation for missing data will be MI (Multiple Imputation); the MI procedure of the SAS system will be used to generate sets of data with missing values imputed from observed data. Total EASI score will be imputed in this manner.

For the imputation of the primary endpoint, where a MI approach is described, the continuous EASI score between 0 and 72 will be multiple imputed, and subsequently the (percentage) change from baseline will be calculated for each imputation in order to derive the categorical outcome of EASI 75. The number of imputations will be 100 for the MI step, representing the set of 100 plausible values obtained from a prediction model based primarily on observed data. The number of imputations and/or burn-in iterations may be increased if there are convergence issues.

Note that all patients in the FAS will be included in the imputation steps below. As previous dupilumab exposure is one of the stratification factors to be included in the MI models, imputation will be in part based on this factor. For analysis, the specific population will then be selected from this total pool of FAS patients with complete data.

The full MI approach will comprise steps as follows:

- Composite Variable Strategy Step (1 imputation): Any missing data to be handled using a composite variable strategy will be imputed using a BOCF approach.
- Multiple imputation Step (100 imputations): After setting to missing any data to be handled using a hypothetical strategy, impute any missing data with a Markov Chain Monte-Carlo (MCMC) multiple imputation approach.
- Combining Step: Rubin's rule (SAS PROC MIANALYZE) is used to combine the 100 point estimates and standard errors, in order to provide a single point estimate, confidence interval and p-value that can be compared to the respective null hypotheses to provide rejection or acceptance.

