6.3.1.1. BOCF Approach for Composite Variable Handling Strategy

Monotone missing data implementing the composite variable strategy will be imputed using a BOCF approach, whereby any missing data occurring on or after ICE of death will be singularly imputed using the available baseline result for the patient. If no observed baseline result is immediately available, then the imputed value from Step 1 will be used and carried forward.

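### The main-estimand imputation steps apply baseline-carried-forward only to missing data, so observed EASI after rescue is left in place, against the SAP's own estimand rule

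*SAP*

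**What the plan says.** **The rule.** SAP 6.1.1 defines three intercurrent events up to Week 16. ICE1 and ICE2 are treatment discontinuation for reasons other than, and because of, lack of efficacy. The third is "ICE3: Patient receives rescue medication prior to Week 16 (either allowed or prohibited) for treatment of AD". For ICE2 and ICE3 the main-estimand entry is "Composite Strategy: Set to baseline"; for ICE1 it is a hypothetical strategy with values set to missing. Protocol Table 10 and the SAP 6.3 imputation table agree. None of the three limits the baseline rule to missing values. The clinical question concerns the difference "in successful responses after 16 weeks achieved without use of rescue medication and if all patients continued with treatment", except for those who stopped for lack of efficacy.

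**The steps.** SAP 6.3.1 gives the procedure for the primary and key secondary endpoints. Its composite step reads: "Any missing data to be handled using a composite variable strategy will be imputed using a BOCF approach". Its multiple-imputation step begins: "After setting to missing any data to be handled using a hypothetical strategy, impute any missing data with a Markov Chain Monte-Carlo (MCMC". SAP 6.3.1.1 then describes the carry-forward itself: "any missing data occurring on or after ICE of death will be singularly imputed using the available baseline result for the patient". It continues: "If no observed baseline result is immediately available, then the imputed value from Step 1 will be used and carried forward".

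**What happens after rescue.** SAP Appendix 3 classes high or ultra-high potency TCS as rescue. Protocol 9.9.4 keeps users of high-potency TCS on study drug, with all visits and efficacy assessments continuing.

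**The concern.** The rule acts on an event; the step acts on a gap in the data. The two give the same result only when every value after ICE2 or ICE3 is missing. After topical rescue the normal case is the opposite, because the patient remains in the trial and the Week 16 EASI is recorded. A programmer working from the step list would leave that value alone, and a patient at EASI 75 with rescue would enter the primary analysis as a responder.

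This procedure serves the one endpoint that decides study success (SAP 7.9), and the key secondary endpoints use the same steps. The pairing of the estimands also suffers. For binary endpoints the main and second estimands are meant to differ only in ICE1 and in missing data unrelated to an intercurrent event. With the gap they would differ in rescue as well, and the comparison could no longer isolate the effect of discontinuation.

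The death wording in SAP 6.3.1.1 is a secondary fault. Death is not among ICE1 to ICE3, and that section names neither ICE2 nor ICE3.

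**Working it through.** **Side-by-side reading**

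| Place | Data affected | Overrides observed values? |
|---|---|---|
| SAP 6.1.1, SAP 6.3 table, Protocol Table 10 | all values after ICE2 or ICE3 | yes, no limit to missing |
| SAP 6.3.1, composite step | missing values under the composite strategy | not stated |
| SAP 6.3.1, multiple-imputation step | values under the hypothetical strategy (ICE1) | yes, first set to missing |
| SAP 6.3.1.1 | monotone missing values from death onward | no |
| SAP 6.3.2 (second estimand) | all values after rescue or discontinuation | yes, by event through Week 16 |

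Within the step list, only the hypothetical strategy carries an instruction to overwrite observed data. SAP 6.3.2 shows the SAP stating an event-based override in its operational text, but only for the second estimand. SAP 6.3.1 does send missing composite-strategy values to carry-forward before MCMC, so 6.3.1.1 conflicts with it rather than clearly diverting those values to MCMC. The Step 1 baseline imputation that 6.3.1.1 cites is not described: the first bullet in 6.3.1 is the carry-forward step itself. SAP Section 11 lists no change to the handling of intercurrent events, so the 6.1.1 rule still appears to be the intended one.

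**Planned power.** Inputs from SAP 4.3: 208 and 104 patients, 55% versus 30%, two-sided 5%. Normal approximation with pooled null variance:

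- Pooled rate = (208 × 0.55 + 104 × 0.30)/312 = 0.4667
- SE0 = √[0.4667 × 0.5333 × (1/208 + 1/104)] = 0.0599
- SE1 = √[0.55 × 0.45/208 + 0.30 × 0.70/104] = 0.0566
- Power = Φ[(0.25 − 1.96 × 0.0599)/0.0566] = Φ(2.34) = 99.0%

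This agrees with the stated figure of more than 95%.

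**Effect of keeping observed post-rescue values.** The documents give no rescue rate and no response rate after rescue, so these are assumptions:

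- the planned 55% and 30% already count rescue as non-response;
- rescue is 10, 15 or 20% on placebo (pP) and 5 or 10% on lebrikizumab (pL);
- a share r of 25% or 50% of rescued patients is at EASI 75, the same in both arms.

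New rate per arm = planned rate + rescue rate × r. Change in difference = r × (pL − pP).

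| pP | pL | r | Difference (points) | Power |
|---|---|---|---|---|
| 10% | 5% | 25% | 23.75 | 98.2% |
| 10% | 5% | 50% | 22.5 | 96.8% |
| 10% | 10% | 25% | 25.0 | 99.0% |
| 10% | 10% | 50% | 25.0 | 98.9% |
| 15% | 5% | 25% | 22.5 | 96.9% |
| 15% | 5% | 50% | 20.0 | 92.0% |
| 15% | 10% | 25% | 23.75 | 98.1% |
| 15% | 10% | 50% | 22.5 | 96.7% |
| 20% | 5% | 25% | 21.25 | 94.9% |
| 20% | 5% | 50% | 17.5 | 83.5% |
| 20% | 10% | 25% | 22.5 | 96.8% |
| 20% | 10% | 50% | 20.0 | 92.0% |

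In the worst row the rates are 0.55 + 0.05 × 0.50 = 57.5% and 0.30 + 0.20 × 0.50 = 40.0%. The patients reclassified are 104 × 0.20 × 0.50 = 10.4 on placebo and 208 × 0.05 × 0.50 = 5.2 on lebrikizumab. Unpooled variance gives 84.3% for this row.

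Heavier rescue would cost more: 30% and 10% with r = 50% gives 60.0% versus 45.0%, a difference of 15.0 points and power of 71.0%.

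If r may differ by arm within the grid, the shift runs from 0.05 × 0.25 − 0.20 × 0.50 = −8.75 points to 0.10 × 0.50 − 0.10 × 0.25 = +2.5 points.

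**The case against.** The strongest reply is that the rule is stated and the steps only word it badly. SAP 6.1.1 and the 6.3 table give the baseline rule and the set-to-missing rule as parallel instructions; if one overrides observed values, so does the other. The SAP also uses the term missing data loosely. SAP 6.3.2 introduces non-responder imputation as a way to handle missing data and then applies it to every rescued patient. On that reading the composite step means all ICE2 and ICE3 data.

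Further points are fair:

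- The exposed group is mainly topical-rescue patients. Systemic rescue requires stopping study drug (Protocol 8.3.2 and 9.9.4), after which Week 16 EASI would often be missing and the composite step covers it.
- The size rests wholly on assumed rates.
- The example code is redacted, so the programs may already be right.

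All of this stands as far as it goes. The intended rule can be recovered, and nothing is claimed about the code. It does not remove the conflict: the step list is the detailed instruction, and two competent programmers could reach different primary results from it. The protocol does not settle the matter, since Protocol 11.2 lets the SAP prevail where they differ and the conflict lies inside the SAP. The blind data review (SAP 5.3) could catch the gap before unblinding, but its general wording supplies no rule.

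**Conclusion.** The concern holds. As written, the main-estimand steps in SAP 6.3.1 do not carry out the rule in SAP 6.1.1, and SAP 6.3.1.1 contradicts both. Programmed literally, the primary analysis would count responses reached after rescue and would not answer its stated question.

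The size is unknown. Under the assumed rates with equal post-rescue response in the two arms, the difference moves by 0 to −7.5 points and power lies between 83.5% and 99.0%. These powers are unadjusted and assume that the planned rates already treat rescue as non-response. With more rescue on placebo, the result is a shifted estimand and lost power. An inflated effect needs the opposite imbalance, or a better post-rescue response on lebrikizumab; the grid allows at most +2.5 points. The matter must be settled before unblinding, because choosing between the readings afterwards would be a post-hoc decision about the primary result.

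**What to change.** Amend SAP 6.3.1 and 6.3.1.1 before unblinding:

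- Replace the composite step with wording such as: *From the first ICE2 or ICE3 through Week 16, all values, observed or missing, are replaced by the baseline value before the MCMC step and are not imputed by MCMC; values after ICE1 are set to missing and multiply imputed.* Add that ICE2 or ICE3 takes precedence when a patient also has ICE1, in either order. Carrying the rule through Week 16 mirrors SAP 6.3.2; the SAP does not currently say this for the main estimand.
- In 6.3.1.1, replace the reference to death with ICE2 and ICE3. State separately which intercurrent event and strategy apply to a death before Week 16. If the phrase were simply deleted, a death would apparently fall under "ICE1: Patient prematurely discontinues study treatment due to reasons other than lack of efficacy prior to Week 16" and be multiply imputed.
- Describe the Step 1 baseline imputation or remove the reference.
- Check that the programs for the primary and key secondary endpoints match the amended text.

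The cost is a few sentences and a program check. No new data are needed.

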6.3.1.1. BOCF Approach for Composite Variable Handling Strategy

Monotone missing data implementing the composite variable strategy will be imputed using a BOCF approach, whereby any missing data occurring on or after ICE of death will be singularly imputed using the available baseline result for the patient. If no observed baseline result is immediately available, then the imputed value from Step 1 will be used and carried forward.

6.3.1.2. Markov Chain Monte-Carlo (MCMC)

Any patient with missing data for EASI score will be multiple imputed using a MCMC approach, with multiple chains, including factors for study treatment, stratification factors, baseline EASI score, and binary variables for ICE occurrence at the visit. At this point, 100 imputations will be available for the primary estimand.

Example SAS syntax is as follows:

CCI

[figure not shown]

This document is confidential.

6.3.1.3. Combining Step (Rubin's Rule)

SAS Proc MIANALYZE will be used to combine the 100 point estimates (per estimand) for the difference in percentage of patients achieving EASI 75 response at Week 16 between treatments and standard errors, allowing appropriate statistical inference as described below:

CCI

6.3.2. Nonresponder Imputation

The nonresponder imputation (NRI) method will be used to handle missing data relative to the supportive estimand for binary/categorical endpoints (composite). Patients who receive rescue medication or discontinue treatment, will be set to non-response subsequent to this time through Week 16. Intermittent missing values will also be set to non-response.

The nonresponder imputation (NRI) method imputes missing values as non-responders and can be justified based on the composite strategy (ICH E9R1) for handling intercurrent events. In this strategy patients are defined as responders only if they meet the clinical requirements for response at the predefined time AND they remain on the assigned study treatment (ie not using rescue medications and not having missing values due to other reasons). Failing either criteria by definition makes them nonresponders.

Randomized patients without at least 1 post-baseline observation will also be defined as nonresponders for all visits for the NRI analysis.

[figure not shown]
6.3.3. Mixed-effects Model for Repeated Measures

Mixed Model for Repeated Measures analyses will be performed on continuous endpoints to mitigate the impact of missing data. This approach assumes missing observations are missing-at-random (missingness is related to observed data) and borrows information from patients in the same treatment arm taking into account both the missingness of data through the correlation of the repeated measurements.

When MMRM is used, the model includes treatment, baseline value, visit, the interaction of the baseline value-by-week, the interaction of treatment-by-week, and the stratification factors mentioned in [Section 7.5](#) as fixed factors.

Example SAS syntax is as follows:

CCI

This document is confidential.

7. General Aspects for Statistical Analysis

